6.0 Treatment Plan

	Study entry ^a	INDUCTI ON: (up to 2 Cycles) *At each treatment [*]	INDUCTION CYCLE 1		INDUCTION CYCLE 2 (**if needed as indicated by bone marrow aspirate and biopsy)			CONSOLIDATION : (up to 4 Cycles for CBF AML) *At each treatment*	Post- treatment	Follow-up or relapse			
			*Additional Activities*		*Additional Activities*					*Additional Activities*			
			Day 4	Day 14 (+/- 2 days)	Prior	Day 3	Day 14 (+/- 2 days)						
Informed consent	X												
Demographics	X												
Medical history	X												
Concurrent meds	X												
Physical exam	X												
Vital signs	X	X							X				
Height, Weight, M ²	X												
Performance Status	X												
Bone marrow aspirate & biopsy ^b	X			X ^b			X ^b			X ^b			
CBC w/diff, platelets	X	X							X	X			
Serum chemistry ^c	X ^d	X							X				
Troponin I (Appendix E)	X ^d		X ^e			X ^e							
B-HCG ^f	X												
ECHO (Appendix E)	X ^h				X ^g					X ^g			
MRI without contrast (Appendix E)	X									X	X		
Adverse event evaluation	X	X	X	X	X	X	X	X	X	X	X		

^a Completed within 28 days prior to registration unless otherwise indicated.

^b On day 14 (+/- 2 days) of Induction Cycles 1 and 2, at recovery to confirm response, and at completion of all treatment, then as clinically indicated.

^c Total bilirubin, BUN, creatinine, SGOT[AST], SGPT[ALT]

^d Draw after consent signed and prior to day 1 treatment; results not required to start treatment.

^e On day 4 of treatment of Induction Cycle 1, and on day 3 of Induction Cycle 2 for those with persistent leukemia.

^f Serum pregnancy test (women of childbearing potential).

^g Limited ECHO with strain measures

^h Full 3D ECHO

CYTARABINE PLUS CONTINUOUS INFUSION DAUNORUBICIN, WITH CARDIAC MRI MONITORING, INDUCTION THERAPY FOR ADULTS WITH ACUTE MYELOID LEUKEMIA; A FEASIBILITY STUDY

Wake Forest Baptist Comprehensive Cancer Center (WFBCCC) CCCWFU 22616

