3.0 Patient Selection

3.1 Inclusion Criteria

- 3.1.1 Patients must have morphologically confirmed newly diagnosed acute myelogenous leukemia (AML) with blood or bone marrow disease. Patients with only extramedullary disease in the absence of bone marrow or blood involvement are eligible. Note: This protocol uses WHO diagnostic criteria for AML. Patients with acute promyelocytic leukemia (APL, FAB, M3) or blastic transformation of chronic myelogenous leukemia (CML) are not eligible.
- 3.1.2 ≥ 18 years of age.
- 3.1.3 ECOG performance status 0-3.
- 3.1.4 Patients with ECHO EF $\geq 45\%$ within 28 days prior to registration.
- 3.1.5 Because of the teratogenic potential of the drugs used in this study, women of child-bearing potential and men must agree to use adequate contraception (hormonal or barrier method of birth control; abstinence) prior to study entry and for the duration of study participation. Should a woman become pregnant or suspect she is pregnant while participating in this study, she should inform her treating physician immediately.
- 3.1.6 Ability to understand and the willingness to sign an IRB-approved informed consent document.

CYTARABINE PLUS CONTINUOUS INFUSION DAUNORUBICIN, WITH CARDIAC MRI MONITORING, INDUCTION THERAPY FOR ADULTS WITH ACUTE MYELOID LEUKEMIA; A FEASIBILITY STUDY

Wake Forest Baptist Comprehensive Cancer Center (WFBCCC) CCCWFU 22616

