3.2 Exclusion Criteria

- 3.2.1 Patients who have received prior induction chemotherapy for AML or MDS. Temporary prior measures such as apheresis or hydroxyurea are allowed. Patients who have received a limited and short-term exposure of ATRA (all trans retinoic acid) while AML-M3 (Acute Promyelocytic Leukemia) was being ruled out, and which has been discontinued, will be eligible.
- 3.2.2 Patients receiving any other investigational agents.
- 3.2.3 Patients with prolonged QTc interval (> 500 msec) determined by EKG within 28 days prior to registration.
- 3.2.4 Patients not suitable for cardiac MRI. Contraindications include:
 - Intracranial metal, pacemakers, defibrillators, functioning neurostimulator devices, or other implanted electronic devices
 - Ferromagnetic cerebral aneurysm clips, or other intraorbital/intracranial metal
 - Allergy to Gadolinium or other severe drug allergies
 - Claustrophobia
 - Congestive heart failure (NYHA class III or IV)
 - Significant valvular disease, or significant pulmonary disease requiring supplemental oxygen therapy
- 3.2.5 History of allergic reactions attributed to compounds of similar chemical or biologic composition to daunorubicin or cytarabine.
- 3.2.6 Patients with documented CNS involvement.
- 3.2.7 Patients who are known to be HIV+ may be eligible providing they meet all of the following additional criteria within 28 days prior to registration:
 - CD4 cells \geq 500/mm³
 - Viral load of < 50 copies HIV mRNA/mm³ if on cART or < 25,000 copies HIV mRNA if not on cART
 - No zidovudine or stavudine as part of cART

Patients who are HIV+ and do not meet all of these criteria are not eligible for this study.
- 3.2.8 Patients with other uncontrolled intercurrent illness or psychiatric illness/social situations that would limit compliance with study requirements.
- 3.2.9 Pregnant women are excluded from this study because of the potential for teratogenic or abortifacient effects with drugs used in this study. Because there is an unknown but potential risk for adverse events in nursing infants

CYTARABINE PLUS CONTINUOUS INFUSION DAUNORUBICIN, WITH CARDIAC
MRI MONITORING, INDUCTION THERAPY FOR ADULTS WITH ACUTE MYELOID
LEUKEMIA; A FEASIBILITY STUDY

Wake Forest Baptist Comprehensive Cancer Center (WFBCCC) CCCWFU 22616

secondary to treatment of the mother with the drugs used in this study, breastfeeding should be discontinued prior to beginning treatment.

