4.0 Registration Procedures

All patients entered on any WFBCCC trial, whether treatment, companion, or cancer control trial, **must** be registered with the WFBCCC Protocol Registrar or entered into ORIS Screening Log within 24 hours of Informed Consent. Patients **must** be registered prior to the initiation of treatment.

You must perform the following steps in order to ensure prompt registration of your patient:

1. Complete the Eligibility Checklist (Appendix B)
2. Complete the Protocol Registration Form (Appendix A)
3. Alert the Cancer Center registrar by phone, *and then* send the signed Informed Consent Form, Eligibility Checklist and Protocol Registration Form to the registrar, either by fax or e-mail.

Contact Information:

Protocol Registrar [contact]

Protocol Registrar [contact]

Protocol Registrar E-MAIL ([contact])

*Protocol Registration is open from 8:30 AM - 4:00 PM, Monday-Friday.

4. Fax/e-mail ALL eligibility source documents with registration. Patients **will not** be registered without all required supporting documents.

Note: If labs were performed at an outside institution, provide a printout of the results. Ensure that the most recent lab values are sent.

To complete the registration process, the Registrar will:

- assign a patient study number
- register the patient on the study

CYTARABINE PLUS CONTINUOUS INFUSION DAUNORUBICIN, WITH CARDIAC
MRI MONITORING, INDUCTION THERAPY FOR ADULTS WITH ACUTE MYELOID
LEUKEMIA; A FEASIBILITY STUDY

Wake Forest Baptist Comprehensive Cancer Center (WFBCCC) CCCWFU 22616

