Appendix B – Subject Eligibility Checklist

IRB Protocol No.	WFBCCC Protocol No. 22616
Study Title: Cytarabine plus Continuous Infusion Daunorubicin Induction Therapy for Adults with Acute Myeloid Leukemia; A Feasibility Study with Cardiac MRI Monitoring	
Principal Investigator: [name]	

Inclusion Criteria (as outlined in study protocol)	Criteria is met	Criteria is NOT met	Source Used to Confirm * (Please document dates and lab results)
Patients must have morphologically confirmed newly diagnosed acute myelogenous leukemia (AML) with blood or bone marrow disease. Patients with only extramedullary disease in the absence of bone marrow or blood involvement are eligible. Note: This protocol uses WHO diagnostic criteria for AML. Patients with acute promyelocytic leukemia (APL, FAB, M3) or blastic transformation of chronic myelogenous leukemia (CML) are not eligible.			
≥ 18 years of age.			
ECOG performance status 0-3.			
Patients with ECHO EF ≥ 45% within 28 days prior to registration.			
Women of child-bearing potential and men must agree to use adequate contraception (hormonal or barrier method of birth control; abstinence) prior to study entry and for the duration of study participation. Should a woman become pregnant or suspect she is pregnant while participating in this study, she should inform her treating physician immediately.			
Women of child-bearing potential and men must agree to use adequate contraception (hormonal or barrier method of birth control; abstinence) prior to study entry and for the duration of study participation.			
Ability to understand and willingness to sign an informed IRB-approved informed consent document			

**CYTARABINE PLUS CONTINUOUS INFUSION DAUNORUBICIN, WITH CARDIAC
MRI MONITORING, INDUCTION THERAPY FOR ADULTS WITH ACUTE MYELOID
LEUKEMIA; A FEASIBILITY STUDY**

Wake Forest Baptist Comprehensive Cancer Center (WFBCCC) CCCWFU 22616

Exclusion Criteria (as outlined in study protocol)	Criteria NOT present	Criteria is present	Source Used to Confirm * (Please document dates and lab results)

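### The only pregnancy test is timed to registration, not to the first dose, so a negative result 28 or more days old can be accepted when daunorubicin and cytarabine start

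*Combined protocol and SAP*

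**What the plan says.** The calendar in Section 6.0 marks B-HCG once, in the study-entry column. No later column carries a mark.

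- Footnote f, attached to B-HCG, says who is tested and by what method: "Serum pregnancy test (women of childbearing potential"). It gives no timing.
- Footnote a, attached to the study-entry column, therefore governs: "Completed within 28 days prior to registration unless otherwise indicated".
- Footnote d is the one footnote that ties a study-entry sample to the start of treatment: "Draw after consent signed and prior to day 1 treatment; results not required to start treatment". It is attached to serum chemistry and troponin I, not to B-HCG.
- Section 4.0 says patients must "be registered prior to the initiation of treatment". This fixes the order of events but not the interval between them.
- Criterion 3.2.9 reads: "Pregnant women are excluded from this study because of the potential for teratogenic or abortifacient effects with drugs used in this study". It names no test and no test date. The same criterion says "breastfeeding should be discontinued prior to beginning treatment".
- Criterion 3.1.5 says "women of child-bearing potential and men must agree to use adequate contraception" and asks a woman who suspects pregnancy to tell her physician.
- The pregnancy row of the Appendix B checklist repeats 3.2.9, again with no test date. The checklist does have a source column headed with the instruction "Please document dates and lab results".

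**The concern.** The exclusion protects a fetus from exposure to the study drugs, so what matters is whether the woman is pregnant when the infusion begins. The test that supports the exclusion is instead dated backwards from registration, an administrative event that may come days before dosing. A woman who conceives after the test, or too shortly before it for the test to be positive, can meet every written requirement and still receive drugs that the protocol itself describes as teratogenic.

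Within 3.2.9, the breastfeeding instruction is tied to the start of treatment while the pregnancy test is not. Footnote d shows that the authors could tie a blood sample to day 1 when they wished to.

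Any harm would be rare but could be irreversible. The statistical analysis is not affected.

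**Working it through.** The plan states no figure for the age of the test at first dose, so there is none to reproduce. The check is a reading of the timing rules followed by simple arithmetic.

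**Inputs**

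- Test to registration: at most 28 days (Section 6.0, footnote a, because footnote f is silent on timing).
- Registration to day 1: g days, with g ≥ 0 (Section 4.0, order only). No upper limit is given.

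**Could another rule cap g?**

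- The 24-hour rule in Section 4.0 runs from consent to registration or screening-log entry. It does not reach the first dose.
- Section 6.1 gives doses and days for induction but no date by which induction must start.
- The 14-day limit in Section 6.1 applies to starting consolidation after recovery from induction.

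None of these limits the time from registration to the first induction dose.

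**Oldest permitted test at first dose**

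Maximum age = 28 + g days. The values of g are assumptions, because the documents give none.

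| g (assumed) | Maximum test age now | Maximum age with a window of w = 3 / 7 / 14 days before day 1 (assumed) | Reduction for w = 7 |
|---|---|---|---|
| 0 | 28 + 0 = 28 | 3 / 7 / 14 | 28 − 7 = 21 |
| 7 | 28 + 7 = 35 | 3 / 7 / 14 | 35 − 7 = 28 |
| 14 | 28 + 14 = 42 | 3 / 7 / 14 | 42 − 7 = 35 |

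A window anchored to day 1 caps the age at w whatever g is.

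**Effect of the test's own blind spot**

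If a test cannot detect a conception in the last d days before it is drawn, the span of undetected conceptions before day 1 is at most 28 + g + d now and w + d under the change. The difference is (28 + g + d) − (w + d) = 28 + g − w. Thus d cancels, and the reduction in the last column holds whatever d is.

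**Number of women concerned**

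Section 3.3 plans for at least 18 women among 40 participants. The documents do not say how many are of childbearing potential, how old their tests would be, or how long they would wait for treatment. The number exposed cannot be estimated.

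**The case against.** The strongest reply is that the worst case is unlikely. These are newly diagnosed AML patients treated as inpatients, so the gap from registration to treatment is probably short. Section 6.2 also suggests that laboratory work takes place around enrollment. This is plausible, but the 28-day look-back remains even at g = 0, and Section 6.2 does not name the pregnancy test.

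Other safeguards exist. Criterion 3.2.9 excludes pregnant women outright, whatever the test shows; 3.1.5 requires agreement to contraception; the treating physician signs the checklist; and a note in Section 4.0 asks for the most recent laboratory values when an outside laboratory was used. These reduce the risk. They do not close it, because an early pregnancy may go unrecognised and nobody is required to check the age of the test on day 1.

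Three further points stand in part:

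- Registration-anchored 28-day windows are the protocol's general convention (ejection fraction, QTc, HIV criteria). The contrast with the breastfeeding clause is therefore a sign of the gap rather than an inconsistency in itself.
- A shorter window still misses a very recent conception. As shown above, it narrows the exposure without eliminating it.
- No document supports 7 days in particular, and making the first dose wait for a result is a real cost in AML. The figure belongs to the investigators, and the wait falls only on women whose test is out of window.

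**Conclusion.** The concern holds. As written, the plan accepts a pregnancy test up to 28 + g days old at the first dose of daunorubicin and cytarabine: at least 28 days, and 35 or 42 days if the gap is 7 or 14. The conclusion rests on footnote f giving no timing and on the absence of any limit on g in the protocol text and appendices. The values of g are assumptions, but the 28-day minimum for the oldest permitted test is not.

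In practice the effect is small. The number of women exposed cannot be calculated and is expected to be very low. No endpoint, sample size or analysis is touched. The change is worth making because the possible harm is serious and the remedy is cheap.

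**What to change.** Amend footnote f so that women of childbearing potential must have a negative serum pregnancy test within 7 days before day 1 of induction, with the result known before the first dose. The 7 days is a proposal; the investigators should set the figure.

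- Keep the study-entry test for the eligibility checklist, and repeat it only if it falls outside the window on day 1.
- Print the same window in criterion 3.2.9 and in the pregnancy row of Appendix B. No new checklist field is needed, since the source column already asks for dates and results.
- A repeat sample can share the pre-treatment chemistry and troponin draw. Do not simply attach footnote d to B-HCG: that footnote lets treatment start without the result and sets no number of days.

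The cost is one revised footnote and matching text in two places. A few women with older tests are retested, and their first dose waits for that result. No visit is added.

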6.1 Treatment Administration

Treatment will be administered on an inpatient basis. Reported adverse events and potential risks are described in Section 9. No investigational or commercial agents or therapies other than those described below may be administered with the intent to treat the patient's malignancy.

Agent	Dose	Route	Schedule	Cycle Length
Induction				
Cytarabine	100 mg/m ² /day	IV infusion	Days 1-7	14 days
Daunorubicin	60 mg/m ² /day	IV infusion	Days 1-3	
Re-induction (if needed)				
Cytarabine	100 mg/m ² /day	IV infusion	Days 1-5	14 days
Daunorubicin	60 mg/m ² /day	IV infusion	Days 1-2	
Consolidation (up to 3 cycles, or up to 4 cycles for CBF AML)				
Cytarabine	<60 yrs: 3,000 mg/m ² /day ≥ 60 yrs: 1,500 mg/m ² /day	IV infusion over 3 hours, every 12 hours	Days 1,3,5	≥ 28 days

Induction: This study regimen will follow the standard 7+3 regimen of cytarabine and daunorubicin, with the modification of daunorubicin administered as continuous infusion rather than bolus. Baseline troponin I, full 3D ECHO, and MRI without contrast will be performed prior to treatment.

For troponin determination, the study will use either the TnI-Ultra™ assay, Siemens, Munich Germany or the Beckman Coulter Access 2 AccuTnI+3 assay for detection of troponin I. While the assays are comparable, every effort will be made to test all samples on the current Institutional standard troponin I testing platform (TnI-Ultra assay, Siemens). If the TnI-Ultra assay becomes unavailable either because of changing Institutional standards or product availability the Beckman Coulter Access 2 AccuTnI+3 assay will be utilized. The brand of assay and results will be recorded for each test on the Cardiac Function Worksheet.

Patients will have a bone marrow aspirate and biopsy on day 14 (± 2 days).

Re-induction: A second induction course may be given if the day 14 bone marrow aspirate and biopsy shows bone marrow cellularity as $\geq 10\%$ and $> 5\%$ leukemic blasts. Those requiring re-induction will undergo a limited ECHO with strain measures prior to treatment. This abbreviated cycle will consist of cytarabine on days 1-5 and daunorubicin on days 1 and 2, with a troponin I measure on day 3 and a bone marrow biopsy on day 14 (± 2 days). Patients not achieving a remission after 2 induction attempts will be removed from study.

CYTARABINE PLUS CONTINUOUS INFUSION DAUNORUBICIN, WITH CARDIAC
MRI MONITORING, INDUCTION THERAPY FOR ADULTS WITH ACUTE MYELOID
LEUKEMIA; A FEASIBILITY STUDY

Wake Forest Baptist Comprehensive Cancer Center (WFBCCC) CCCWFU 22616

Patients without bone marrow involvement at diagnosis will receive a second induction course if they have not cleared their soft tissue disease by day 14 (± 2 days).

If cellularity is $<10\%$ on day 14, a repeat bone marrow biopsy should be obtained as clinically indicated. Treatment response will be evaluated once ANC $>1,000 / \mu\text{L}$ and platelets $\geq 100,000 / \mu\text{L}$, but no later than day 42. If peripheral blood counts are inadequate (ANC $<1,000 / \mu\text{L}$, platelets $<100,000 / \mu\text{L}$) at the time of this bone marrow aspirate and biopsy, a repeat bone marrow aspirate and biopsy must be obtained to document complete remission at the time of peripheral blood count recovery (ANC $\geq 1,000 / \mu\text{L}$, platelets $\geq 100,000 / \mu\text{L}$) if > 1 week after "day 42" bone marrow study.

Physicians should consider earlier bone marrow exams in patients whose peripheral blood counts are not recovering or recovering sluggishly, as well as in patients whose day 14 bone marrow was suspicious for residual leukemia.

Consolidation: Patients in remission will receive high-dose cytarabine (days 1, 3, and 5) consolidation therapy for up to 3 cycles (except in the case of toxicity or receipt of stem cell transplant). Patients with core-binding factor (CBF) AML may receive 4 cycles of consolidation therapy. Therapy should be started as soon as possible (and within 14 days) after recovery from induction/re-induction therapy.

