6.5 Duration of Therapy

Treatment under this protocol may continue until one of the following criteria applies:

- Allogeneic stem cell transplant,
- Disease progression,
- Intercurrent illness that prevents further administration of treatment,
- Unacceptable adverse event(s),
- Patient decides to withdraw from the study, or
- General or specific changes in the patient's condition render the patient unacceptable for further treatment in the judgment of the investigator.

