7.0 Dose Modifications

Induction: no dose reductions allowed.

Re-induction: Dose reductions may be allowed in the setting of hepatotoxicity as follows:

- For SGPT/SGOT 150-300 U/L **OR** bilirubin 1.5-3.0 mg/dL, reduce daunorubicin dose to 45 mg/m²/day.
- For SGPT/SGOT > 300 U/L **OR** bilirubin > 3.0-5.0 mg/dL, reduce daunorubicin dose to 30 mg/m²/day.

Consolidation: No dose reductions allowed for Cycle 1 except in the instance of renal dysfunction, as follows:

- For creatinine greater than 2 mg/dL or calculated creatinine clearance of < 50 mL/min, decrease cytarabine dose to 1,000 mg/m²/dose.
- For creatinine greater than 3 mg/dL or calculated creatinine clearance of < 30 mL/min, change cytarabine to 400 mg/m²/day IV infusion over 24 hours daily for 5 days.

For consolidation cycles beyond Cycle 1, doses of cytarabine may be reduced by 750 mg/m²/day for the following reasons:

- Grade 3-4 non-hematologic toxicity
- Severe life-threatening infection

If toxicity persists, cytarabine dose may be reduced by an additional 750 mg/m²/day.

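### The consolidation cytarabine dose is stated per day but scheduled every 12 hours, so the protocol leaves a two-fold dose ambiguity that the section 7.0 reductions do not resolve

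*Combined protocol and SAP*

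**What the plan says.** The consolidation row of the table in section 6.1 has the dose as "<60 yrs: 3,000 mg/m ² /day ≥ 60 yrs: 1,500 mg/m ² /day" and the route as "IV infusion over 3 hours, every 12 hours", on days 1, 3 and 5. The prose of the same section adds only this: "Patients in remission will receive high-dose cytarabine (days 1, 3, and 5) consolidation therapy for up to 3 cycles". It qualifies this with "except in the case of toxicity or receipt of stem cell transplant". Patients with core-binding factor AML may have a fourth cycle.

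Section 7.0 sets the reductions for consolidation:

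- Cycle 1: "No dose reductions allowed for Cycle 1 except in the instance of renal dysfunction".
- First renal threshold (creatinine above 2 mg/dL or clearance below 50 mL/min): "decrease cytarabine dose to 1,000 mg/m²/dose". No frequency is given.
- Second renal threshold (creatinine above 3 mg/dL or clearance below 30 mL/min): 400 mg/m²/day as a 24-hour infusion for 5 days.
- After Cycle 1, for grade 3-4 non-hematologic toxicity or severe infection: "doses of cytarabine may be reduced by 750 mg/m²/day for the following reasons". A further 750 mg/m²/day may come off if toxicity persists.

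**The concern.** A 12-hourly schedule means two infusions on each dosing day. A per-day figure beside it can be read in two ways: as a total to be split between the two infusions, or as the amount of each infusion with the wrong unit attached. This row is the only place where the starting dose for consolidation is given.

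Section 7.0 then uses both units, per dose in the first renal rule and per day in the others. If the units are taken at face value, the first renal rule is not a decrease for patients aged 60 and over. Such patients can enter: section 3.1 sets no upper age limit, and section 3.2 has no creatinine or clearance exclusion.

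This is a matter of patient safety. Section 9.2 warns of severe and sometimes fatal toxicity with high-dose cytarabine, so a starting dose that can be read two-fold apart should not stand.

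**Working it through.** The plan gives no per-cycle total to reproduce, so the check is to carry each reading through the schedule and the reduction rules.

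**Inputs.** Section 6.1: 3,000 mg/m² (under 60) and 1,500 mg/m² (60 and over); one infusion every 12 hours; dosing days 1, 3 and 5. Section 7.0: 1,000 mg/m² per dose; 400 mg/m²/day for 5 days; steps of 750 mg/m²/day.

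**Infusions per cycle.** 24/12 = 2 per dosing day; 2 × 3 days = 6.

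**Starting dose.** On the daily-total reading, each infusion is the tabled figure divided by 2. On the per-infusion reading, each infusion is the tabled figure. The cycle dose is 6 times the infusion.

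| Age | Reading | Per infusion (mg/m²) | Per dosing day | Per cycle |
|---|---|---|---|---|
| <60 | daily total | 3,000/2 = 1,500 | 3,000 | 9,000 |
| <60 | per infusion | 3,000 | 6,000 | 18,000 |
| ≥60 | daily total | 1,500/2 = 750 | 1,500 | 4,500 |
| ≥60 | per infusion | 1,500 | 3,000 | 9,000 |

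The ratio is 2 in both age groups.

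**First renal rule.** Assume that 12-hourly dosing continues. The reduced dose is 1,000 × 6 = 6,000 mg/m² per cycle.

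- Daily total: 6,000/9,000 − 1 = −33% (<60); 6,000/4,500 − 1 = +33% (≥60), that is, 1,000 against 750 mg/m² per infusion.
- Per infusion: 6,000/18,000 − 1 = −67% (<60); 6,000/9,000 − 1 = −33% (≥60).

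If 1,000 mg/m² were instead given once per dosing day, the ≥60 result on the daily-total reading would be 1,000/1,500 − 1 = −33%. The increase therefore depends on the frequency being kept. That is the natural reading, because the first rule changes only the dose while the second states a new schedule, but the text does not say so.

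**Second renal rule.** 400 × 5 = 2,000 mg/m² per cycle. This is a decrease in all four cases, from −56% (against 4,500) to −89% (against 18,000).

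**Toxicity steps, at 750 mg/m²/day as written, ≥60.** Daily total: 1,500, then 750, then 0 mg/m²/day. Per infusion: 3,000, then 2,250, then 1,500 mg/m²/day. The zero disappears on the per-infusion reading, but only while the step stays per day. If the step were also meant per dose, it would run 1,500, 750, 0 mg/m² per infusion.

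**Does any other text settle the unit?**

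- The other rows of the dose column are also per day, and sections 10.2 and 10.3 describe those drugs as 24-hour infusions. There the figure is a true daily total, which supports the literal reading.
- The high-dose label in section 6.1 and the per-dose unit of the first renal rule point to the per-infusion reading.
- Section 9.2 describes high-dose schedules of 2.0 to 3.0 g/m² at 12-hour intervals. This is adverse-event background and matches only the under-60 figure.
- Section 10.3 does not mention a 3-hour infusion at all.

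None of these prescribes the trial's consolidation dose.

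**The case against.** The best reply is that the intent is clear enough. Most cues point to a per-infusion dose, and on that reading the first renal rule works in both age groups. A reading that turns an instruction to decrease into an increase is a reason to reject the reading. It is not a second, separate defect. That argument stands as evidence of intent. It does not remove the problem: if per infusion was meant, the per-day unit in section 6.1 is wrong and understates the daily dose by half; if a daily total was meant, the renal rule fails at 60 and over. Something needs correcting either way.

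A reader might go further and infer that the protocol directs a higher dose for older patients with renal impairment. The documents do not support that. The 33% needs the less likely reading and an assumed 12-hourly frequency. The rule also says to decrease, so a prescriber already giving 750 mg/m² could not obey it by moving to 1,000; the realistic outcome is a query or no reduction. Nor must such a patient continue, since section 6.1 excepts toxicity and section 6.5 allows stopping for unacceptable adverse events, intercurrent illness or the investigator's judgment.

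It is also fair to say that consolidation is background therapy and not the intervention under study. A reader might infer damage to the trial's results, but there is no basis for that here. The section 13.3 figures (0.511 SD and ±0.181 at n=32) do not use the cytarabine dose, and no effect on the cardiac or disease-free survival results is shown.

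**Conclusion.** The unit conflict in the consolidation row is real and leaves the dose ambiguous by a factor of two: 9,000 or 18,000 mg/m² per cycle under 60, and 4,500 or 9,000 mg/m² at 60 and over. High confidence applies to the conflict and to that range only.

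The renal finding is conditional. If the figure is a daily total and 12-hourly dosing continues, a patient aged 60 or over who meets only the first renal threshold has no usable decrease in Cycle 1. This makes the per-infusion reading more likely but does not prove it. The toxicity steps are permissive and decide nothing, though their resulting doses should be stated. That two prescribers would in fact dose differently is a possibility that the text leaves open, not something the documents show.

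**What to change.** The clinical team should confirm the intended dose and then:

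- Restate the section 6.1 cell in one unit. The likely wording is 3,000 mg/m² (<60) or 1,500 mg/m² (≥60) per dose, every 12 hours, 6 doses per cycle.
- State every consolidation reduction in section 7.0 in the same unit, with the frequency and with the resulting dose, or an explicit stop, at each step for each age group.
- If a daily total is intended, set the first renal step for patients aged 60 and over below 750 mg/m² per infusion.

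The cost is a protocol clarification or amendment covering one table cell and the units in section 7.0, plus a check of the order set against the corrected text. No patients, visits or procedures are added, and the statistical section needs no change.
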